3.4 Assignment of Analysis Sets to Analysis

Primary efficacy analysis will be based on the FAS. A sensitivity analysis of the primary endpoint will be performed using the PP set. All secondary efficacy outcomes will exploratorily be analyzed using the FAS and PP set. Safety analyses will be based on the SAF.

4 Statistical Evaluation

The investigator will review the patient's diary and enter the number of days with headache and the number of days with migraine in the eCRF. This information will be available for the baseline period, the performance assessment period and the follow-up period.

In case a patient should have documented less than 28 days per period (but has a compliance of at least 80%), the number of headache days per period is derived as follows:

Number of headache days = (Number of headache days x 28) / Number of days observed

If a patient has a diary compliance of less than 80%, this period will not be used for statistical analysis of this endpoint.

For example, if a patient documented 24 days for one period only, and documented 6 days with headache, the derived number of headache days in this period is calculated to $(6 \times 28) / 24 = 7$.

The assessments done before start of treatment will serve as baseline evaluations. Generally, a baseline measurement refers to the last non-missing assessment made before treatment start.

Continuous data are presented with the number of observations, mean value, standard deviation (SD), minimum, 1st quartile (Q1), median, 3rd quartile (Q3), and maximum value. Categorical data are presented as counts and percentages. In general, minimum and maximum will be presented to the same level of precision as the raw data; means and medians, SD, and quartiles will be presented to one further decimal place. Categorical variables will be presented by frequency tables, using number and percentage. Percentages will be presented to one decimal place.

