4.3 Performance Analysis

For all tests, a two-sided significance level of 5% ($\alpha = 0.05$) will be applied.

Analysis for the primary performance endpoint will be based on the FAS. Additionally, a sensitivity analysis of the primary endpoint will be performed using the PP.

All statistical tests for secondary performance endpoints are considered exploratory and no adjustment for multiplicity is made.

All secondary endpoints will be evaluated for the performance assessment period and the follow-up period.

The 4-week screening period is defined as Baseline.

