4.3.1 Analysis of Primary Performance Variable

Mean change from Baseline in 4-week headache days

The mean change from Baseline (4-week screening period) in 4-week headache days with moderate to severe intensity in 4-week performance assessment period (V3 to V7) will be analyzed as follows:

The primary null hypothesis to be tested is

$H_0: \mu_{\text{active}} = \mu_{\text{placebo}}$ against the alternative

$H_1: \mu_{\text{active}} \neq \mu_{\text{placebo}}$,

where μ is the mean change from Baseline (4-week screening period) in 4-week headache days with moderate to severe intensity in 4-week performance assessment period (V3 to V7).

An analysis of covariance (ANCOVA) with treatment, baseline number of headache days, medication overuse as independent variables will be calculated to test above null hypothesis. Check for the normal distribution of data will be performed.

Normality of data cannot be assumed, if at least one of the following items can be demonstrated on the residuals, as determined when applying the ANCOVA as described above:

- p-value using Shapiro-Wilk test on normality < 0.2 .
- Visual check of the QQ-plot shows: plotted points do not approximately lie on the diagonal line $y = x$.

If normality of data cannot be shown, it can be assumed that the data are approximately normal distributed due to the large sample size, i.e. the results of ANCOVA can be implemented in the group-sequential design.

A group-sequential design with O'Brien & Fleming alpha spending function allows adjustment of alpha using spending function according to the information fraction at the interim analysis

available, so that the overall significance level alpha of 0.05 is considered for evaluation at the final analysis.

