4.3.2 Analysis of Secondary Performance Variables

The analyses of the secondary performance variables will be performed using the FAS. All statistical tests will be considered exploratory and no adjustment for multiplicity will be made.

Mean change from Baseline in 4-week headache in follow-up period

The mean change from Baseline in 4-week headache days in follow-up period will be similarly analyzed as the primary performance endpoint for the performance assessment period. If the data is normally distributed an ANCOVA will be calculated to test above null hypothesis. If the data is not normally distributed the van Elteren test will be used with medication overuse as stratification to test above null hypothesis.

The analysis for the performance assessment period is covered by the primary analysis.

Mean change from Baseline in 4-week migraine days

The mean change from Baseline in 4-week migraine days will be similarly analyzed as the primary performance endpoint; however, the number of migraine days instead of number of headache days will be counted. If the data is normally distributed an ANCOVA will be calculated to test above null hypothesis. If the data is not normally distributed the van Elteren test will be used with medication overuse as stratification to test above null hypothesis.

Mean change from Baseline in 4-week headache days (mild, moderate and severe intensity) in 4-week performance assessment period (V3 to V7)

The mean change from Baseline in monthly headache days with mild to severe intensity will be similarly analyzed as the primary performance endpoint; however, the number of headache days with mild intensity will be included. If the data is normally distributed an ANCOVA will be calculated to test above null hypothesis. If the data is not normally distributed the van Elteren test will be used with medication overuse as stratification to test above null hypothesis.

Proportion of subjects with 30% or greater reduction in headache days

The proportion of subjects with 30% or greater reduction from baseline period to performance assessment period and to follow-up period will be presented descriptively using frequency tables

summarizing the number and percentage of patients with a headache reduction of 30% or greater.

Additionally, active and placebo treatment arms will be compared using a Chi-square test. In case of less than 5 subjects per group, the Fisher's exact test will be used.

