Proportion of subjects with 50% or greater reduction of headache days

The proportion of subjects with 50% or greater reduction from baseline period to performance assessment period and to follow-up period will be presented descriptively using frequency tables summarizing the number and percentage of patients with a headache reduction of 50% or greater.

Additionally, active and placebo treatment arms will be compared using a Chi-square test. In case of less than 5 subjects per group, the Fisher's exact test will be used.

Change in the use of acute (abortive) medication

Information about the use of abortive medication is given in the patient diary. The number of days with abortive medication will be summed up per 4-week period.

The absolute 4-week use of abortive medication and change from Baseline in 4-week use of abortive medication will be presented by descriptive statistics.

Headache impact test-6 (HIT-6)

The total HIT-6 score and change from Baseline will be presented by descriptive statistics. The number and percentage of patients in each category will be presented for each of the 6 items. The total HIT-6 score change from Baseline will be tested using a Wilcoxon rank sum test.

All HIT-6 items must be answered to receive a total HIT-6 score. The total HIT-6 score will be calculated as the weighted sum of answers. The answers are weighted with points as follows:

Answer	Point
Never	6
Rarely	8
Sometime	10
Very often	11
Always	13

Further details of HIT-6 handling are described in user's guide (Bayliss & Batenhorst, 2002).

In tables and listings the HIT-6 items will be labeled as follows:

Question No.	Question Text in CRF	Label for listings and tables
1.	When you have headaches, how often is the pain severe?	Level of severe pain
2.	How often do headaches limit your ability to do usual daily activities including household work, work, school, or social activities?	Activity
3.	When you have a headache, how often do you wish you could lie down?	Tiredness
4.	In the past 4 weeks, how often have you felt too tired to do work or daily activities because of your headaches?	Fatigue
5.	In the past 4 weeks, how often have you felt fed up or irritated because of your headaches?	Psychological distress
6.	In the past 4 weeks, how often did headaches limit your ability to concentrate on work or daily activities?	Cognitive function

Migraine-specific quality of life questionnaire (MSQ)

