The 3 dimensions of the MSQ will be presented by descriptive statistics for absolute values and changes from Baseline. The changes from Baseline will be tested using a Wilcoxon rank sum test for each of the 3 dimensions.

The scoring of the MSQ items is completed in 3 steps:

1. Recoding of MSQ items

The MSQ items are worded with a negative perspective, therefore they must be recoded before the domain scores are calculated.

Item Number	Response categories Precoded	Precoded item value	Final item value
1-14	None of the time	1	6
	A little bit of the time	2	5
	Some of the time	3	4
	A good bit of the time	4	3
	Most of the time	5	2
	All of the time	6	1

2. Computation of raw domain scores: the algebraic sum of the final item value for all items in that domain:

Domain	Cluster of Items
Role function - Restrictive	1 - 7
Role function - Preventive	8 - 11
Emotional function	12 - 14

3. Transformation of raw domain scores to a 0 to 100 scale.

Domain	Raw score range	Transformation formula
Role function - Restrictive	7 to 42	(raw score - 7)*100/35
Role function - Preventive	4 to 24	(raw score - 4)*100/20
Emotional function	3 to 18	(raw score - 3)*100/15

Further details of MSQ scaling and scoring as well as handling of missing data are described in manual (Mapi Research Teust, 2017).

Patient global impression of severity (PGI-S)

The score will be presented descriptively using frequency tables. The change from Baseline will be assessed with a shift table of baseline versus post-baseline assessments.

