The listings are always sorted by treatment group, center, and subject. If a different sorting order should be used for some listings this will be remarked separately. The variables for the special listings are explicitly given in the description of listings. All listings will be presented for the safety analysis set, if not stated differently, and indicator variables for further analysis sets, e.g., full analysis set, will be added.

Screened but not treated subjects (e.g. withdrawal before treatment) will be considered in tables and listings describing disposition of subjects, analysis sets and discontinuation as well as listings for subject demographics and migraine history.

The following title will be used for all generated tables, listings, and graphs:

PM007 – Final Analysis

Page # of #

<Subtitle for description of contents - if applicable>

<Analysis set>

The numbering NNN of the tables/listings/graphs will be stated in the detailed description (Appendix A).

Following footnote will be used for all generated tables, listings, and graphs:

Date: <Actual date(ddmmmyyyy)>

Program: <Name of program>

The statistical evaluation will be performed using SAS version 9.4 or higher.

5 Changes from Protocol

- The wording “monthly headache days” was changed to “4-week headache days” in order to avoid confusion. The analysis is based on 4 week (28 day) assessment windows and not on calendar months (30 days).
- For PGI-S no Wilcoxon test for change from baseline will be performed, since this is a categorical parameter.
- Secondary efficacy outcomes will also be analyzed for the PP set.
- An additional unblinded subgroup analysis (the unblinded analysis of the German subjects) will be performed.
- No Van Elteren test will be used for primary performance endpoint if the data is not normally distributed as no adjustment of alpha is possible according to group-sequential design with O’Brien & Fleming alpha spending function. The ANCOVA will be used even if the normal distribution cannot be shown. Due to the large sample size, it can be assumed that the data are approximately normal distributed.

6 Literature

Bayliss, M. S., & Batenhorst, A. S. (2002). *The HIT-6 TM A User's Guide*. Research Triangle Park, NC: QualityMetric Incorporated, Lincoln, RI and GlaxoSmithKline.

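### HIT-6 and MSQ, and possibly three diary secondaries, get no baseline-adjusted treatment difference; add one beside the planned rank tests

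*SAP*

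**What the plan says.** **Questionnaires.** For HIT-6, SAP 4.3.2 states "The total HIT-6 score change from Baseline will be tested using a Wilcoxon rank sum test", and for MSQ "The changes from Baseline will be tested using a Wilcoxon rank sum test for each of the 3 dimensions". No covariate or stratum is named. Protocol 13.2 plans the same tests. Both questionnaires are completed at Screening and again at V1 before randomisation (Protocol 11.5.1 and 11.5.2). Randomisation is stratified by medication overuse (Protocol 11.2.3, SAP 1).

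**Three diary secondaries** (moderate-to-severe headache days in follow-up, migraine days, headache days of any intensity). SAP 4.3.2 says each is analysed like the primary, by ANCOVA if the data are normal. It then adds: "If the data is not normally distributed the van Elteren test will be used with medication overuse as stratification to test above null hypothesis". The only normality rule is in SAP 4.3.1, and I read it as carrying over. Normality fails if Shapiro-Wilk on the ANCOVA residuals gives p < 0.2, or if the QQ plot departs from the diagonal; either is enough.

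**Primary endpoint.** SAP Section 5 removes van Elteren "as no adjustment of alpha is possible according to group-sequential design" and adds: "The ANCOVA will be used even if the normal distribution cannot be shown". SAP 4.3.1 gives the supporting argument: "If normality of data cannot be shown, it can be assumed that the data are approximately normal distributed due to the large sample size".

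**Baseline.** SAP 4 has a general rule: "Generally, a baseline measurement refers to the last non-missing assessment made before treatment start". SAP 4.3 says: "The 4-week screening period is defined as Baseline".

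**Status.** All secondary tests are exploratory, without multiplicity adjustment (SAP 4.3).

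**The concern.** The primary analysis adjusts for baseline and for the stratum. HIT-6 and MSQ have a baseline score and the same stratum, yet their tests use neither as an adjustment and no adjusted difference is planned. The diary secondaries start from the primary's model but can lose the baseline covariate on the outcome of a loose check. The SAP relies on sample size to keep ANCOVA for the primary, and these endpoints come from the same patients.

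Two things are at stake. One is precision: the change score still carries baseline variation that a covariate would remove. The other is interpretability: the report could show an adjusted difference in days for the primary, but only a rank-test p-value and descriptive means for a neighbouring diary endpoint. The primary conclusion is not at stake.

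**Working it through.** **The plan's own figure.** Protocol 13.5 gives 64 per group for a 3-day difference, SD 6, two-sided 0.05 and 80% power. The t-test power is 0.795 at 63 and 0.801 at 64 per group, so 64 reproduces. The group-sequential information of 0.91156 gives 0.91156 × 4 × 36 = 131.26, hence 132, or 66 per arm. There is no sample size or power for any secondary endpoint.

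**Inputs.** From the documents: 66 per arm, two-sided 0.05, and the p < 0.2 gate. Assumed, because the documents give no SD, effect or correlation for these endpoints:
- effect 0.5 SD of change, borrowed from the primary (3/6);
- baseline-to-follow-up correlation ρ from 0.3 to 0.8;
- equal variances at baseline and follow-up;
- half the patients with medication overuse.

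**Formula.** The variance of the treatment effect under ANCOVA, relative to unadjusted change, is (1 − ρ²) / [2(1 − ρ)] = (1 + ρ)/2. That is 0.65, 0.75, 0.85 and 0.90 at ρ = 0.3, 0.5, 0.7 and 0.8. The unadjusted mean comparison has expected z = 0.5 × √(66/2) = 2.87, so power is Φ(2.87 − 1.96) = 0.82. Dividing 2.87 by √0.65, √0.75, √0.85 and √0.90 gives z = 3.56, 3.32, 3.12 and 3.03, and power of about 0.95, 0.91, 0.88 and 0.86.

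**Simulation.** There were 4,000 runs per cell (Monte Carlo SE about √(0.8 × 0.2/4000) = 0.006). Each entry is ANCOVA / Wilcoxon on change / gated procedure, where gated means ANCOVA unless Shapiro-Wilk p < 0.2 and van Elteren otherwise.

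| Residuals | ρ 0.3 | ρ 0.5 | ρ 0.7 | ρ 0.8 | Gate fires |
|---|---|---|---|---|---|
| Normal | 0.934 / 0.782 / 0.896 | 0.909 / 0.794 / 0.882 | 0.871 / 0.794 / 0.855 | 0.844 / 0.789 / 0.835 | 0.186-0.200 |
| t(6) | 0.941 / 0.833 / 0.868 | 0.908 / 0.846 / 0.866 | 0.871 / 0.855 / 0.871 | 0.850 / 0.853 / 0.861 | 0.680-0.706 |
| t(4) | 0.941 / 0.857 / 0.868 | 0.906 / 0.866 / 0.869 | 0.875 / 0.882 / 0.885 | 0.862 / 0.904 / 0.902 | 0.884-0.896 |
| t(3) | 0.938 / 0.896 / 0.896 | 0.903 / 0.914 / 0.911 | 0.882 / 0.934 / 0.932 | 0.870 / 0.947 / 0.948 | 0.968-0.974 |
| Gamma(4) | 0.933 / 0.806 / 0.803 | 0.911 / 0.831 / 0.830 | 0.870 / 0.838 / 0.838 | 0.848 / 0.850 / 0.848 | 0.996-0.997 |

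**Reading the table.**
- With normal residuals, ANCOVA gains between 0.844 − 0.789 = 5.5 and 0.934 − 0.782 = 15.2 points over Wilcoxon.
- On exactly normal residuals the gate fires in about one trial in five, as p < 0.2 implies. It then costs 0.844 − 0.835 = 0.9 to 0.934 − 0.896 = 3.8 points. The QQ-plot criterion was not simulated.
- Off normality, the gated procedure runs from 13 points worse than ANCOVA (gamma, ρ 0.3) to 8 points better (t(3), ρ 0.8).
- In 7 of the 20 cells Wilcoxon equals or beats ANCOVA.

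**Smaller effect.** At 0.4 SD with normal data, Wilcoxon has 0.60 power and ANCOVA 0.81, 0.74 and 0.70 at ρ 0.3, 0.5 and 0.7.

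**Stratum.** Omitting it costs nothing if medication overuse does not affect change. If that effect is 0.25, 0.5 or 1.0 SD, plain Wilcoxon loses about 0-0.5, 2 and 7-8 points against van Elteren.

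**Type I error.** In the null settings simulated at ρ 0.5, all four procedures (ANCOVA, Wilcoxon, van Elteren, gated) stayed between 0.043 and 0.056.

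**The case against.** The strongest case against is that these are valid, pre-specified rank tests on exploratory endpoints, and that choosing between them and ANCOVA is largely preference. The stated cause for removing van Elteren from the primary is group-sequential alpha, which does not concern the secondaries. SAP 4.3.2 writes the switch out separately under each of the three endpoints, in line with Protocol 13.2, so it may be deliberate. The ANCOVA must be fitted to obtain its residuals, and SAP Appendix A, not in the supplied text, may tabulate its estimate. Changing tests after the interim also invites questions, since HIT-6, migraine days and all-intensity headache days are on the futility list in Protocol 13.3.

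Most of this stands. It rules out a demand to replace the tests; it does not supply the missing adjusted estimates. The large-sample argument still applies to both sets of endpoints.

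Stronger readings that the documents do not support:
- *The baseline is ignored.* It enters by subtraction in the change score; it is only not adjusted for.
- *The HIT-6 and MSQ baseline is contradictory.* SAP 1 ties the 4-week baseline to the diary. For a questionnaire completed twice before treatment, the general rule in SAP 4 picks the last score, normally V1. A clarifying clause is enough.
- *ANCOVA will certainly do better.* It does not with heavy tails and high correlation.

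**Conclusion.** The point holds as a low-priority improvement. HIT-6 and the three MSQ domains have no planned analysis adjusted for baseline or stratum, and three diary secondaries can lose theirs through the normality switch. The effect is on precision and interpretability only.

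The power gain of roughly 5 to 15 points rests on normal data, the primary's standardised effect and an assumed correlation, none of which the documents give for these endpoints. The textual finding is firm; the size of the benefit, and in some settings its direction, is not. A reader might infer that the planned p-values are unreliable or that the primary result is weakened. Neither follows: type I error is held, and the primary's ANCOVA does not depend on these tests.

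**What to change.** In SAP 4.3.2, for HIT-6 total, each MSQ domain and the three diary secondaries, add an ANCOVA on change with treatment, baseline value and medication overuse. Run it whatever the normality check shows, and report the adjusted difference with 95% CI beside the planned rank tests. State in one clause that the HIT-6 and MSQ baseline is the last score before treatment, under the general rule in SAP 4. List the addition in SAP Section 5.

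Make the ANCOVA the main analysis of these endpoints only if it is documented that the decision was taken by staff without access to interim or German-subgroup results. This matters because the interim is done (SAP 4.6), SAP 4.3.1 speaks of interim and subgroup analyses in the past tense, and SAP 4.7 sends the German results to an unblinded person at the sponsor. Otherwise keep the planned tests as main and the ANCOVA as supplementary.

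The cost is SAP wording, minor programming and a second result for each of 1 + 3 + 3 = 7 exploratory outcomes. The two results may disagree, so the text should say in advance which one leads. No new data are needed.

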4.4 Safety Analysis

Safety variables will be analyzed based on the SAF.

Adverse events (AEs)

Adverse events will be coded by the Medical Dictionary for Regulatory Activities (MedDRA) version 21.0.

The analysis will be based on treatment emergent AEs (TEAEs), i.e. AEs which started after first treatment. Incidences of TEAEs will be summarized by preferred term (PT) and system organ class (SOC). TEAEs related to the medical device, TEAEs related to procedure, and serious TEAs will be tabulated separately. TEAEs will be summarized also by preferred term (PT), system organ class and intensity. Listings will be generated for TEAEs, serious TEAEs, TEAEs related to procedure or medical device and non-treatment emergent AEs.

4.5 Missing Values

In case of incomplete diary data, the endpoints will be imputed as described in Section 4. In case of incomplete questionnaires data, handling of missing data will be performed as described within corresponding manual. No other missing value imputation methods will be applied.

4.6 Interim Analysis

The interim analysis was carried out and did not lead to stop of the study or to sample size adaption. The study will continue as originally planned.

4.7 Data Base Closure and Data Review

Due to additional unblinded subgroup analysis (the unblinded analysis of the German subjects) two data base closures are foreseen: additional data base closure - a data base closure for additional unblinded subgroup analysis and final data base closure - data base closure for final analysis.

An additional data base closure will be performed prior to the additional unblinded subgroup analysis. All parameters for German subjects only will be checked, as specified in the data validation plan, and all queries resolved before additional data base closure and additional unblinded subgroup analysis.

The blind data review meeting (BDRM) for German subjects only will be conducted prior to additional data base lock based on clean data to verify the number of subjects allocated to the selected analysis sets, needed for additional unblinded subgroup analysis.

These evaluations and assessments will be done together and in agreement with the Sponsor, however FGK will provide the Sponsor with the appropriate excel file including affiliation to the analysis sets. Data review for additional unblinded subgroup analysis will contain data of German subjects only and will be done in writing.

The affiliation of subjects to the SAF and the FAS (German subjects only) will be done prior to unblinding for additional unblinded subgroup analysis. The identification and classification of the protocol deviation observed within the clinical investigation for German subjects as well as affiliation of subjects to the PP will be done during final BDRM.

Data unblinding for German subjects only based on the randomization listing and the additional unblinded subgroup analysis will be done after data review has been conducted and data review minutes have been signed by both the Sponsor and FGK. However, no final unblinding for German subjects will take place for additional unblinded subgroup analysis. Only unblinded FGK team will perform affiliation of subjects to the treatment groups and the additional unblinded subgroup analysis. The results of additional unblinded subgroup analysis will be provided by unblinded FGK team to the unblinded responsible person of Sponsor. The final unblinding of all subjects will be done after final data base closure.

A final data base closure will be performed prior to the final analysis. All parameters will be checked, as specified in the data validation plan, and all queries resolved before final data base closure and final analysis.

The final blind data review meeting (BDRM) will be conducted prior to final data base lock based on clean data to verify the number of subjects allocated to the analysis sets, and to identify and classify the protocol deviation observed within the clinical investigation.

These evaluations and assessments will be done together and in agreement with the Sponsor, however FGK will provide the Sponsor with the appropriate subject listings (as defined in appendix A). Data review can be done via a telephone conference or in writing.

The affiliation of subjects to the SAF, the FAS, and the PP (inclusive German subjects) will be done prior to unblinding.

Data unblinding based on the randomization listing and the final analysis will be done after data review has been conducted and data review minutes have been signed by both the Sponsor and FGK.

The affiliation of subjects to the treatment groups will be done after final unblinding.

4.8 **Miscellaneous**

For qualitative variables the frequencies (absolute and relative) are calculated. If no further remark is given in the description of the tables following format will be used for all tables with qualitative variables:

		Y-variable(s) (e.g., treatment group)				
		Category 1		Category 2		Total
X-variable(s)	N	%	N	%	N	%
category 1	xx	xx.x	xx	xx.x	xx	xx.x
category 2	xx	xx.x	xx	xx.x	xx	xx.x
missing	xx	xx.x	xx	xx.x	xx	xx.x
Total	xx	100.0	xx	100.0	xx	100.0

For this standard format the description of the tables in Appendix A determines only the X- and Y-variables. If another format of table is described in the details to the tables, the real design will be determined by the technical possibilities within SAS and may not look identical to the provided example. However, all information as displayed will be included.

Quantitative parameters will be described by declaring the mean value, standard deviation, minimum, first quartile, median, third quartile, and maximum. In the description of the tables this will be denoted by „basic statistics“.

The listings are always sorted by treatment group, center, and subject. If a different sorting order should be used for some listings this will be remarked separately. The variables for the special listings are explicitly given in the description of listings. All listings will be presented for the safety analysis set, if not stated differently, and indicator variables for further analysis sets, e.g., full analysis set, will be added.

Screened but not treated subjects (e.g. withdrawal before treatment) will be considered in tables and listings describing disposition of subjects, analysis sets and discontinuation as well as listings for subject demographics and migraine history.

The following title will be used for all generated tables, listings, and graphs:

PM007 – Final Analysis

Page # of #

<Subtitle for description of contents - if applicable>

<Analysis set>

The numbering NNN of the tables/listings/graphs will be stated in the detailed description (Appendix A).

Following footnote will be used for all generated tables, listings, and graphs:

Date: <Actual date(ddmmmyyyy)>

Program: <Name of program>

The statistical evaluation will be performed using SAS version 9.4 or higher.

5 Changes from Protocol

- The wording “monthly headache days” was changed to “4-week headache days” in order to avoid confusion. The analysis is based on 4 week (28 day) assessment windows and not on calendar months (30 days).
- For PGI-S no Wilcoxon test for change from baseline will be performed, since this is a categorical parameter.
- Secondary efficacy outcomes will also be analyzed for the PP set.
- An additional unblinded subgroup analysis (the unblinded analysis of the German subjects) will be performed.
- No Van Elteren test will be used for primary performance endpoint if the data is not normally distributed as no adjustment of alpha is possible according to group-sequential design with O’Brien & Fleming alpha spending function. The ANCOVA will be used even if the normal distribution cannot be shown. Due to the large sample size, it can be assumed that the data are approximately normal distributed.

6 Literature

Bayliss, M. S., & Batenhorst, A. S. (2002). *The HIT-6 TM A User's Guide*. Research Triangle Park, NC: QualityMetric Incorporated, Lincoln, RI and GlaxoSmithKline.

